6.5 Concomitant Therapy

Patients will continue on the most recent ARSI on which documented progression was observed. For example, a patient with PSA progression on abiraterone would continue abiraterone and enroll on this trial. For patients that have stopped the most recent ARSI and been treated with another anti-cancer therapy (i.e., progression on abiraterone and then treatment with radium-223), the patient should resume treatment with an ARSI and show documented progression on that treatment before enrolling on this trial. For patients that have stopped an ARSI and then resumed as part of standard of care prior to this trial, a rising PSA is sufficient for eligibility. ARSI's are FDA approved for the treatment of metastatic prostate cancer and will be administered per institutional standards in this study.

All intercurrent medical conditions should be treated by the investigator according to current community standards of care. Subjects may also receive medications for symptomatic relief, such as analgesics, laxatives, anti-emetics, etc.

Subjects who require palliative radiotherapy for focal symptom relief may remain on study as long as the treating investigator feels they are deriving benefit from Sacituzumab Govitecan and the radiotherapy is not to a target or non-target lesion recorded at baseline.

Complementary/alternative therapies which may lower PSA or have an anti-hormonal effect (e.g., saw palmetto, selenium supplements, grape seed extract, etc.) are prohibited.

All medications used during the study and taken within 30 days of the screening visit will be recorded.

6.5.1 *Prohibited medications/treatments*

Any investigational therapies other than Sacituzumab Govitecan.

Any other systemic therapy intended for the treatment of prostate cancer other than Sacituzumab Govitecan, ARSI used on study, and LHRH agonists or antagonists, which the subject must have started at least 3 months prior to study entry if the subject has not undergone orchiectomy.

6.6 Drug Accountability

Sacituzumab Govitecan will be supplied by Gilead Sciences, Inc. The investigator acknowledges that the drug supplies are investigational and, as such, must be used strictly in accordance with the protocol and only under the supervision of the investigator or sub-investigators. No study medication will be sent to the study site until all required regulatory documents, including IRB approval, are received by the sponsor or its representatives.

Adequate records documenting receipt, use, return, loss, or other disposition of study drug vials must be kept. A complete drug accountability record, supplied by Gilead Sciences, Inc. (or its designee or NCI drug accountability forms), or computer records used by the pharmacy at the investigational site, can be used to provide drug accountability. In all cases, information describing study medication supplies and their disposition, subject-by-subject, must be provided and signed by the Investigator (or the pharmacist or other person who dispensed the drug) and collected by the Study Monitor. Requisite data include relevant dates, quantities, batches or code numbers, and subject identification for subjects who received trial product.

The investigator and investigational site staff are responsible for maintaining an accurate inventory and accounting of investigational drug. Receipt and use of Sacituzumab Govitecan will be recorded on an Investigational Drug Inventory Form provided by the sponsor, or site-required form if approved by the sponsor. The investigator will record the following information:

- Date and quantity of Sacituzumab Govitecan received by the site
- Subject number for each subject receiving Sacituzumab Govitecan
- Date and quantity of Sacituzumab Govitecan dispensed to each subject
- Date and quantity of Sacituzumab Govitecan returned to inventory from each subject
- The name of the person dispensing investigational drug
- Each shipment of Sacituzumab Govitecan will be accompanied by an invoice describing the amount of drug shipped to the site. The information on the invoice must be verified against the actual amount of Gilead Sciences, Inc. drug received by the site; the investigator or the investigator's designee will then sign the invoice and place it in the investigator's file.

At each monitoring visit, the monitor will reconcile the information on the Investigational Drug Inventory Form with the actual amount of Sacituzumab Govitecan remaining at each site. At the conclusion of the study, all unused drug supplies must be returned to the sponsor or its designee, or destroyed according to institutional operating standards. Drug accountability will be performed on site by the clinical monitor before destruction, unless approval is given to destroy prior to monitoring. A record of the destruction will be placed in the investigator's file.

Unused investigational product must not be discarded or used for any purpose other than the present study. Investigational product which has been dispensed to a subject and returned unused must not be re-dispensed to a different subject, but may be dispensed to the same subject.

At the end of the study, following authorization by study management, study medication may be destroyed at the site as dictated by the appropriate standard operating procedures at the participating institutions. Destruction must be documented. Alternatively, after notification, all unused products will be collected by the Study Monitor and returned to Gilead Sciences, Inc..

7. SAFETY EVALUATION

7.1 Definitions

7.1.1 *Adverse event (AE)*

All subjects must be carefully monitored for AEs, including clinical laboratory tests. AEs should be assessed in terms of their seriousness, intensity, and relationship to the study drug. For consistency, events are to be graded using the CTCAE version 4.0.

An AE is any untoward medical occurrence in a subject or clinical investigation subject administered a pharmaceutical product, and which does not necessarily have to have a causal relationship with this treatment. An AE can therefore be any unfavorable and unintended sign (including an abnormal laboratory finding, for example), symptom, or disease temporally associated with the use of a medicinal product, whether or not considered related to the medicinal product.

AEs include the following:

1. An exacerbation, or an unexpected increase in frequency or intensity of a pre-existing condition (other than condition under investigation), including intermittent or episodic conditions.
2. Significant or unexpected worsening or exacerbation of the condition/indication under investigation.
3. A suspected drug interaction.
4. An intercurrent illness.
5. Any clinical significant laboratory abnormality.

An AE does not include:

1. Anticipated day-to-day fluctuations of any pre-existing conditions, including the disease under study.
2. Signs and symptoms of the disease under study that do not represent a significant worsening or exacerbation.
3. Expected progression of the disease under investigation.

7.1.2 *Adverse drug reaction*

All noxious and unintended responses to a medicinal product related to any dose should be considered adverse drug reactions (ADRs). The phrase “responses to a medicinal product” means that a causal relationship between a medicinal product and an adverse event is at least a reasonable possibility, i.e. the relationship cannot be ruled out. Causality assessment is required for all clinical investigation cases. All cases judged by either the reporting health care professional or the sponsor as having a reasonable suspected causal relationship to the medicinal product qualify as ADRs.

7.1.3 *Unexpected adverse drug reaction*

An unexpected ADR is an AE where the nature or severity of which is not consistent with the applicable product information (e.g., Investigational Brochure, study protocol or ICF). The following documents or circumstances will be used to determine whether an AE/ADR is expected:

- For a medicinal product not yet approved for marketing in a country, a company's Investigational Brochure, study protocol or ICF will serve as the source document in that country.
- Reports which add significant information on specificity or severity of a known, already documented serious ADR constitute unexpected events. For example, an event more specific or more severe than described in the Investigational Brochure would be considered "unexpected." Specific examples would be (a) acute renal failure as a labeled ADR with a subsequent new report of interstitial nephritis and (b) hepatitis with a subsequent report of fulminant hepatitis.

7.1.4 *Serious Adverse Event (SAE)*

A *serious adverse event (SAE)* or reaction is any untoward medical occurrence that at any dose:

- Is life-threatening (an event in which the subject was at risk of death at the time of the event; it does not refer to an event which hypothetically might have caused death if it were more severe).
- Results in death.
- Requires in-patient hospitalization or prolongation of existing hospitalization.
- Results in persistent or significant disability/incapacity.
- Is a congenital anomaly or birth defect.
- Disabling/incapacitating
- Other important medical events that may not be immediately life-threatening or result in death or hospitalization but may jeopardize the subject or may require intervention to prevent one of the other outcomes listed above. Examples of such events are intensive treatment in an emergency room for allergic bronchospasm; blood dyscrasias or convulsions that do not result in hospitalization; or development of drug dependency or drug abuse. The term "severe" is often used to describe the intensity (severity) of an event; the event itself may be of relatively minor medical significance (such as a severe headache). This is not the same as "serious", which is based on subject/event outcome or action criteria usually associated with events that pose a threat to a subject's life or functioning.
- An SAE does not include: Progression of the underlying disease or hospitalization for a routine clinical procedure as stipulated by the protocol and hospitalization for elective or pre-planned procedure not associated with a precipitating event or non-medical reasons (i.e., social admissions, hospitalizations for social, convenience or respite care).

7.1.5 *Exposure During Pregnancy*

Pregnancy occurring in female partners of male subjects while the male partner is receiving study drug within 120 days after the final dose should be reported within 24 hours of becoming aware of the event.

The investigator should counsel the subject, and in the case of a male subject, the subject's partner, regarding the risks of continuing with the pregnancy and the possible effects on the fetus. If the female partner of a male subject becomes pregnant, the investigator should obtain informed consent of the pregnant partner, if allowable per

local policy, prior to monitoring the pregnancy. Monitoring of the pregnancy in the female partner of the male subject should continue to the conclusion of the pregnancy. The outcome of all pregnancies (including normal births) must be reported. Follow-up information on the status of the infant should be collected and reported until 90 days post-partum, including anomalies diagnosed at birth or within 90 days post-partum, and condition at birth, neonatal illnesses, hospitalizations, and drug therapies. Complications of pregnancy, such as abortion (spontaneous or induced), premature birth, or congenital anomaly are considered SAEs.

The Sponsor must be notified of any subject's partner becoming pregnant during the study or of any spontaneous abortion or of any therapeutic abortion and any pregnancy must be followed until completion or termination of pregnancy, if allowable per local policy. The notification should be performed on the pregnancy form and handled in the same manner as for SAEs. In the case of a live birth, the "normality" of the newborn can be assessed at the time of birth. The "normality" of an aborted fetus can be assessed by gross visual inspection unless pre-abortion laboratory findings are suggestive of a congenital anomaly.

All pregnancies of any subject's partner, from the time of treatment/ allocation through 120 days following cessation of study treatment, or 30 days following cessation of study treatment if the subject initiates new anticancer therapy must be reported by the investigator.

7.2 Documenting Adverse Events

The investigator should elicit information regarding the occurrence of AEs through open-ended questioning of the subject, physical examination and review of laboratory results.

All AEs, whether serious or not, will be described in the source documents and the AE page of the electronic case report form (eCRF). AEs will be reported from the time of signing of informed consent, however AEs captured prior to the initial administration of Sacituzumab Govitecan will not be considered related to study drug. All new events, as well as those that worsen in intensity or frequency relative to baseline, which occur after administration of study drug through the period of protocol-specified follow-up, must be captured. AEs occurring for 30 days after the last dose of study drug must be reported. SAEs, felt by the investigator to be related to study drug, however, must be reported any time the investigator becomes aware of such an event, even if this occurrence is more than 30 days after the last dose of study drug.

Abnormal laboratory values per se need not be reported as AEs. Abnormal laboratory values that result in clinical sequelae, that require intervention, that are deemed clinically significant by the investigator or investigator's designee, that are SAEs, that result in a change in protocol treatment, or that result in study discontinuation should be reported as AEs.

Information to be reported in the description of each AE includes:

- A medical diagnosis of the event (if a medical diagnosis cannot be determined, a description of each sign or symptom characterizing the event should be recorded).
- The date of onset of the event or whether it is ongoing.

- Whether the event is serious or not.
- Action taken in response to the event.
- Action taken with study drug.
- Outcome.

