Nausea	3 (3.7)	10 (3.1)	0	1 (33.3)	14 (3.3)
Vomiting	2 (2.5)	9 (2.8)	0	1 (33.3)	12 (2.9)
General disorders and administration site conditions	12 (14.8)	22 (6.7)	1 (11.1)	1 (33.3)	36 (8.6)
Fatigue	5 (6.2)	10 (3.1)	1 (11.1)	0	16 (3.8)
Pyrexia	5 (6.2)	4 (1.2)	0	0	9 (2.1)
Infections and infestations	7 (8.6)	22 (6.7)			29 (6.9)
Respiratory, thoracic and mediastinal disorders	4 (4.9)	8 (2.4)	0	0	12 (2.9)
Metabolism and nutrition disorders	2 (2.5)	8 (2.4)	0	0	10 (2.4)

Table 3: Adverse Events of \geq Grade 3 Occurring in >5% of Patients

	Any grade	\geqGrade 3	Grade 4	Grade 5
Patients, n (%)	420 (100.0)			
Patients with at least one AE	419 (99.8)	227 (54.0)	70 (16.7)	20 (4.8)
Gastrointestinal disorders	382 (91.0)	87 (20.7)	0	0
Nausea	283 (67.4)	22 (5.2)	0	0
Diarrhea	261 (62.1)	37 (8.8)	0	0

General disorders and administration. site conditions	316 (75.2)	54 (12.9)	0	5 (1.2)
Fatigue	224 (53.3)	41 (9.8)	0	0
Blood and lymphatic system disorders	277 (66.0)	109 (26.0)	49 (11.7)	0
Anemia	171 (40.7)	47 (11.2)	1 (0.2)	0
Neutropenia	171 (40.7)	75 (17.9)	43 (10.2)	0
Febrile neutropenia	25 (6.0)	18 (4.3)	5 (1.2)	0
Metabolism and nutrition disorders	266 (63.3)	76 (18.1)	8 (1.9)	0
Hypophosphatemia	51 (12.1)	22 (5.2)	1 (0.2)	0
Respiratory, thoracic and mediastinal disorders	210 (50.0)	23 (5.5)	6 (1.4)	7 (1.7)
Investigations	204 (48.6)	71 (16.9)	21 (5.0)	0
Neutrophil count decreased	77 (18.3)	41 (9.8)	13 (3.1)	0
WBC count decreased	62 (14.8)	25 (6.0)	9 (2.1)	0
Infections and infestations	179 (42.6)	38 (9.0)	3 (0.7)	2 (0.5)

Responses have been observed in subjects with triple-negative breast cancer (TNBC), small-cell lung cancer, non-small-cell lung cancer, esophageal cancer, urinary bladder, and colorectal cancer.^{37-40,49} Disease stabilization has been observed in many subjects. Since the initial results over 465 subjects (including, 32 colorectal, 147 TNBC, 60 SCLC, 46 urothelial cancer, 55 non-small cell lung cancer (NSCLC), and 52 advanced/metastatic breast cancer (Non-TNBC), have been treated with Sacituzumab Govitecan, the majority at 10mg/kg given on days 1 and 8 in a 21-day cycle.

While Sacituzumab Govitecan has not been combined with ARSIs in prior studies, fatigue is the only anticipated overlapping toxicity between these classes of agents. ARSIs have been combined with chemotherapy agents in other studies and found to be feasible.^{69,70,71}

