- c. ALT or AST >3x ULN and total bilirubin >2x ULN or INR >1.5

Patients with life threatening, grade 3 non-hematologic toxicity regardless of relationship to study drug should discontinue study treatment permanently. Examples include myocardial infarction or stroke.

In the event of other Grade 3 treatment-related toxicity at the time of a scheduled treatment day, the dose will be held and subjects will be assessed at least weekly. If recovery to \leq Grade 1 delays the next dose by only one week, treatment may resume then without dose reduction. If recovery to \leq Grade 1 delays the next dose by 2 or 3 weeks, treatment must be resumed at a reduced dose (Table 7). If treatment on day 8 of a cycle is held, the dose should be skipped and treatment resumed with day 1 of the following cycle. If treatment on day 1 is delayed, the entire cycle should be delayed, maintaining the same cycle number. The use of prophylactic G-CSF in subsequent cycles is recommended to prevent recurrence of neutropenia that would require a dose reduction. If recovery to \leq Grade 1 requires more than a three-week delay, treatment must be permanently discontinued.

After **cycle 1 day 1** treatment initiation should be withheld until ANC is $> 1000 / \mu\text{L}$. If day 8 is held for ANC $< 1000 / \mu\text{L}$, that dose will be missed. Resume dosing with next cycle. If delay more than 4 weeks, discontinue treatment. GCSF prophylaxis prior to cycle 2 is recommended if clinically appropriate.

For grade ≥ 3 neutropenia (ANC $< 1000 / \mu\text{L}$) after cycle 1 day 1 or after day 1 of subsequent cycles, hold day 8, initiate growth factor support and administer prophylactic growth factors with each subsequent cycle. Resume dosing with the next cycle only if toxicity resolves. **In subsequent treatment cycles**, treatment initiation for Day 1 of the cycle should be withheld until ANC $> 1000 / \mu\text{L}$ and GROWTH FACTORS should be used as clinically indicated. Patient will be assessed weekly for grade 3 ANC (ANC $< 1000 / \mu\text{L}$ to $500 / \mu\text{L}$) and bi-weekly for grade 4 ANC (ANC $< 500 / \mu\text{L}$). If delay more than 3 weeks, discontinue. Resume dosing at the next cycle if toxicity recovers to \leq grade 2 within 3 weeks. All subsequent cycles should be administered with growth factor support.

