7.4.3 Recording information on AEs

All AEs, whether observed by the Investigator, elicited from, or volunteered by the subject, will be recorded including: duration, severity, relationship to the study medication, treatment, action taken with respect to the study medication and outcome. When possible, all events should be reported in diagnostic terms or the most acceptable medical terms in order to interpret safety information accurately.

The investigator must review all laboratory test data and record any AEs. The same format will be used as for other AEs, regardless whether related to study therapy or not, including event severity grading, attribution, and resolution. A summary listing of all AEs occurring during the past year on this study will be provided in progress reports reported to regulatory authorities.

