8.4.2 Safety Analysis

The Safety Analysis Set will consist of all subjects who received at least 1 dose of Sacituzumab Govitecan.

Safety parameters will include results of AE reporting, physical exam findings, vital signs, safety laboratory determinations and ECGs. AEs will be listed according to the MedDRA coding dictionary by system organ class, preferred term and high level terms. All AEs will be classified by type, severity, and causality. In addition to all AEs, SAEs, drug-related AEs, Grade 3 or higher AEs, drug-related Grade 3 or higher AEs, and AEs leading to discontinuation or death will be described. A customized drug dictionary will be used to classify concomitant medications by therapeutic class and preferred term.

Changes from baseline assessments (e.g., laboratory parameters, vital signs and ECG parameters) will be presented using descriptive statistics. The distribution of the maximum observed grade of each AE will be tabulated. Toxicities will be summarized by type and severity in tabular format. Toxicity rates (Grade 2, Grade 3, Grade 4, Grade \geq 2, Grade \geq 3, etc.) will be calculated and reported along the corresponding 95% confidence intervals. The 95% confidence intervals will be constructed using the Wilson score method.

The safety analyses will be stratified by subjects who continued single agent ARSI in combination with Sacituzumab Govitecan and patients who discontinued single agent ARSI before starting Sacituzumab Govitecan.

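### Section 8.4.2 plans neither a pooled neutropenia term nor a laboratory-graded ANC table, so no planned output gives the share of men with neutropenia, and Grade 2 rates may depend on site reporting habits

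*Combined protocol and SAP*

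**What the plan says.** Analysis (section 8.4.2). "AEs will be listed according to the MedDRA coding dictionary by system organ class, preferred term and high level terms". The same section tabulates the maximum grade for each AE and promises rates for Grades 2, 3 and 4, and for Grade 2 or higher and 3 or higher, with 95% Wilson intervals. Safety is stratified by whether the ARSI was continued. For laboratory data the plan is: "Changes from baseline assessments (e.g., laboratory parameters, vital signs and ECG parameters) will be presented using descriptive statistics". No pooled term and no CTCAE grade derived from laboratory values is mentioned.

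Reporting (section 7). Section 7.2 states: "Abnormal laboratory values per se need not be reported as AEs". Its next sentence lists exceptions: values with clinical sequelae, needing intervention, judged clinically significant, meeting SAE criteria, and those "that result in a change in protocol treatment, or that result in study discontinuation should be reported as AEs". Section 7.1.1 counts as an AE "Any clinical significant laboratory abnormality". Section 7.4.3 adds: "The investigator must review all laboratory test data and record any AEs".

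Management (sections 6.4 and 6.4.1). For Grade 3 or higher neutropenia after day 1 the instruction is "hold day 8, initiate growth factor support and administer prophylactic growth factors with each subsequent cycle". Day 1 of a later cycle waits until the ANC exceeds 1000/µL. Section 6.4 also calls for growth factors when the ANC begins to fall.

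Data. Appendix B schedules a CBC with differential on day 1 and day 8 of every cycle; a day 15 CBC is at the physician's discretion.

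Earlier experience (section 1.3, Table 3, 420 patients). The event appears on two rows: neutropenia under blood and lymphatic disorders, and "Neutrophil count decreased" under investigations.

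**The concern.** Neutropenia was the dose-limiting toxicity at 18 mg/kg (section 1.3) and is the most frequent individual Grade 3 or higher term in Table 3. Safety and tolerability is a secondary objective, and section 1.3 says the drug had not previously been combined with an ARSI. A reader of the final report will want to know what share of men had neutropenia, and at what grade.

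Two features of the plan may keep that number from being readable. First, a low neutrophil count can be coded under either of two terms in different system organ classes, and nothing says they will be combined with each man counted once. Second, some low counts enter the AE data only through an investigator's judgement, while the laboratory values that would settle the grade uniformly are reduced to change from baseline. The Grade 2 and Grade 2 or higher hematologic rates, and the description by ARSI stratum, could then reflect coding and reporting habits as well as toxicity.

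**Working it through.** **The plan's own precision figure.** Section 8.3 says that 45 subjects give a standard error below 8% and a 95% interval no wider than 30% for toxicity rates.
- Largest SE = √(0.5 × 0.5 / 45) = 7.45%.
- Largest 95% width at n = 45 = 28.0% (Wilson) or 2 × 1.96 × 7.45% = 29.2% (Wald).

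Both statements reproduce.

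**Effect of the term split (section 1.3, Table 3, N = 420).** With *a* patients under one term and *b* under the other, the number with either lies between max(*a*, *b*), full overlap, and *a* + *b*, no overlap. The table does not give the overlap.

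| Grade | Neutropenia | Count decreased | Pooled range |
|---|---|---|---|
| Any | 171 (40.7%) | 77 (18.3%) | 171 to 248 (40.7% to 59.0%) |
| ≥3 | 75 (17.9%) | 41 (9.8%) | 75 to 116 (17.9% to 27.6%) |
| 4 | 43 (10.2%) | 13 (3.1%) | 43 to 56 (10.2% to 13.3%) |

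Reading only the larger Grade ≥3 row misses between 0% and 41/116 = 35% of affected patients. Table 2 of section 1.3 has the same split for treatment interruption: 87 and 38 of 420, so 20.7% to 125/420 = 29.8%.

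**Carried to this trial's size, at the Table 3 rates.**
- n = 45: 0.179 × 45 ≈ 8 men (17.8%, Wilson 9.3% to 31.3%), up to 0.276 × 45 ≈ 12 men (26.7%, 16.0% to 41.0%).
- n = 55: about 10 men (18.2%, 10.2% to 30.3%), up to about 15 (27.3%, 17.3% to 40.2%).

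The SE of a 17.9% rate at n = 45 is √(0.179 × 0.821 / 45) = 5.7%. The largest possible gap, 9.8 points, is about 1.7 times that.

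**Which laboratory values can go unreported.** Reading 7.2 against 6.4, 6.4.1 and Appendix B:
1. *Grade ≥3 ANC on a scheduled treatment day.* Section 6.4.1 requires a hold. A hold changes protocol treatment, so 7.2 requires an AE. No gap.
2. *Grade 2 ANC on a treatment day.* The footnote to Table 7 puts Grade 2 above 1000/mm³, and treatment is withheld only until the ANC exceeds 1000/µL. A Grade 2 count therefore normally forces no hold. Starting growth factor for a falling ANC would be an intervention and make the value reportable. But a man already on prophylaxis, which 6.4 requires at cycle 1 from age 65, may need no new intervention. Reporting then rests on clinical significance as judged by the investigator.
3. *Low counts between visits.* A count on the discretionary day 15 CBC that recovers before the next day 1, and prompts no action, rests on the same judgement.

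The documents give no laboratory-graded rate, so the size of items 2 and 3 cannot be computed.

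**The case against.** The strongest reply has four parts.

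*Serious neutropenia is already captured.* The mandated hold and growth factor, with the exceptions in 7.2, make Grade 3 or higher neutropenia on a treatment day an AE. This stands. A reader might infer from the first sentence on laboratory values in 7.2 that a Grade 3 or 4 ANC can drop out of the safety tables; on treatment days the documents do not allow that.

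*Splitting a term loses no event.* Both rows stay in the listing, and 8.4.2 also speaks of summarising toxicities by type and severity without saying that rates are computed by preferred term. This stands in part: nothing is deleted, and a single-term headline rate is an inference. But two rows cannot be added without knowing the overlap, and system organ class totals mix in other events.

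*Table 3 shows coding in earlier studies.* Section 7.4.1 here directs sites to CTCAE terms, which might make coding more uniform. That is possible, but the plan neither says that only one term will be used nor states a pooling rule.

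*Laboratory grades have their own gap.* Day 15 sampling is discretionary, so a nadir between visits can be missed, and replacing AE-based rates with day 1 and day 8 values could drop neutropenia found on other CBCs. This stands, and is why the laboratory table should use every post-dose CBC and sit beside the AE table.

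**Conclusion.** The point holds as a gap in the specification of 8.4.2. No planned table gives the share of men with neutropenia under either term, and no laboratory-derived grade is planned although neutrophil counts are collected. At the Table 3 rates the Grade 3 or higher figure could read 17.9% where the pooled figure is anywhere from 17.9% to 27.6%: about 8 versus up to 12 of 45 men. Separately, Grade 2 and Grade 2 or higher hematologic rates may depend on site reporting habits, by an amount the documents do not allow one to size.

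A reader might go further and say that neutropenia will be under-counted, or that the rates and the contrast between ARSI strata are biased low. The documents do not support this. The 35% shortfall is an upper bound that needs zero overlap and a reader who ignores the second row. The stratified analysis is descriptive, and any under-reporting could differ between strata in either direction.

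Assumptions: coding in this trial may split as it did in Table 3, and that table's Grade ≥3 column is as labelled. If the column held Grade 3 only, Grade 3 plus 4 would be 118/420 = 28.1% and 54/420 = 12.9%, pooled 28.1% to 172/420 = 41.0%, with the same conclusion.

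**What to change.** Amend section 8.4.2 in two places.

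(a) Pre-specify pooled terms for the AE tables: neutropenia with neutrophil count decreased, and the corresponding pairs for anemia, leukopenia and thrombocytopenia. Count each man once, at his worst grade.

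(b) Beside the AE-based rates, not in place of them, report each man's worst post-dose CTCAE grade for ANC, WBC, hemoglobin and platelets from all scheduled and unscheduled CBCs. Give Wilson intervals and baseline-to-worst shift tables, overall and by ARSI stratum.

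The cost is a few lines of SAP text and a few more tables; no new assessments are needed. Reported hematologic rates may rise. The laboratory table should carry a note that a nadir between visits can still be missed because the day 15 CBC is discretionary.
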